4.2.1.5 Sensitivity Analyses of the Primary Endpoint

The eight primary endpoints, as described in section [4.2.1.1](#), may be analyzed separately for the following, to show robustness around the specified intercurrent event strategies.

- Excluding participants who discontinue treatment
- Excluding participants who initiate any another medication, in line with IPDs listed in the PD specification.

4.2.2 Secondary Endpoint

4.2.2.1 Definition

The secondary objective is to assess the PK and immunogenicity, which will be done through serum trough tezepelumab concentrations and ADA. The analyses of the secondary endpoints will use the PK analysis set for the PK summaries and the safety analysis set for the ADA summaries.

4.2.2.2 Derivations

Due to the limited sampling schedule, the PK assessment will be based on the observed serum trough concentrations.

ADA assessments will be conducted utilizing a tiered approach (screen, confirm, titer).

For ADA and PK results reported as lower than the LLOQ, a value equal to half of the LLOQ will be imputed and used for analysis purposes.

4.2.2.3 Handling of Dropouts and Missing Data

If informed consent/assent to the study was withdrawn, all data up until the date of withdrawn informed consent/assent will be included.

4.2.2.4 Primary Analysis of Secondary Endpoint

4.2.2.4.1 Analysis of pharmacokinetics

The PK analyses will be performed by a third-party vendor under the guidance of AstraZeneca Research and Development.

Tezepelumab serum concentrations will be summarized using descriptive statistics at each visit. The following criteria will apply for data to be included in the summary table:

- Only samples collected prior to the first study intervention dose for baseline samples
- Only samples collected prior to influenza vaccination administration for pre-vaccination samples

For descriptive statistics of tezepelumab concentrations:

- If, at a given time point, 50% or less of the concentrations are non-quantifiable (NQ), the geometric mean, geometric coefficient of variation (GCV), arithmetic mean and SD will be calculated by substituting the LLOQ divided by 2 for values which are NQ.
- If more than 50%, but not all, of the concentrations are NQ, the geometric mean, GCV, arithmetic mean and SD will be reported as not calculable (NC)
- If all the concentrations are NQ, the geometric mean and arithmetic mean will be reported as NQ and the GCV and SD as NC

- The median, minimum and maximum will also be reported.

The LLOQ of tezepelumab in serum will be 0.010 µg/mL.

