^e For women of childbearing potential only, urine HCG test to be completed at study site on each study visit (before study intervention administration on Visit 3 to Visit 6).

^f PK and ADA to be collected PRIOR to study intervention dose at Visit 3 and PK to be collected PRIOR to influenza vaccination at Visit 6.

^g Blood draw for serum antibodies to influenza vaccine should occur prior to administration of influenza vaccine. If influenza vaccine administration is delayed from Visit 6 (Week 12), pre-influenza vaccine blood draw for serum antibodies should only occur on the week of influenza vaccine administration.

^h Influenza vaccine is to be administered at a different site than study intervention and site of injection noted. Participant is to be observed for 15 minutes after injection and before administering study intervention. Influenza vaccine is to be administered after scheduled blood samples are taken and prior to study intervention administration.

ⁱ If influenza vaccine administration is delayed, an additional 1 to 2 unscheduled study intervention visits may occur prior to Visit 6, until the influenza vaccine is available at study sites. All assessments during the unscheduled visit may not be necessarily completed.

Abbreviations: **CCI** ADA=anti-drug antibodies; AE=adverse event; CSP=clinical study protocol; EOT=end of treatment; FU=follow-up; HCG=human chorionic gonadotropin; IPD=investigational product discontinuation; PK=pharmacokinetics; Unsch=unscheduled; V=visit; W=week.

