for influenza A and 2 for influenza B) selected for the influenza season 2021/2022 for the northern hemisphere will be used ([FDA 2021](#)).

Immunogenicity will be assessed using 2 types of strain-specific assays (dual primary endpoint) detecting vaccine humoral response:

- Hemagglutinin inhibition (HAI) assay and microneutralization (MN) assay.

Hemagglutinin inhibition assay measures the ability of serum to block haemagglutination, which is the aggregation of red blood cells caused by influenza virus. The resulting haemagglutination inhibition antibodies titer is a correlate of protection for influenza virus that is accepted by many regulatory agencies. Microneutralization assay detect antibodies that directly neutralize virus ([Hannoun et al 2004](#), [Hobson et al 1972](#), [Krammer 2019](#)).

The dual primary endpoint includes seroconversion outcome measures (4-fold rise in titer and titer $\geq 1:40$) provided as response rates, and central measures of tendency for the immune response (geometric mean fold rises [GMFR] and geometric mean titers [GMT]) for the HAI and MN assay results. For the Influenza A H3N2-strain, only the MN assay will be performed owing to the known low hemagglutination effect of the strain ([Sicca et al 2020](#)).

In this study, a functional response of the immune system to the influenza vaccine will be assessed in adolescents and young adults with moderate to severe asthma. The rationale for selecting this population is based on the previous similar study with anti-IL5 biologic drug benralizumab in which humoral immune response was assessed in adolescent and young adult (12 to 21 years old) severe asthmatics ([Zeitlin et al 2018](#)). A total of 103 participants were randomized and received benralizumab (n=51) or placebo (n=52). There were no consistent differences in HAI or MN antibody responses 4 weeks after the inactive quadrivalent influenza vaccine administration between participants receiving benralizumab or placebo.

Participant entry will be stratified by age (12 to 17-year age group and 18 to 21-year age group) to ensure equitable distribution of treatment allocation for analysis.

In addition to the immune response to vaccine, the tezepelumab impact on [CCI](#) [REDACTED] number of exacerbations, serum trough tezepelumab concentrations, and anti-drug antibodies (ADAs) will be investigated.

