3.3.2 Visit Window

All summaries and analyses which are presented by visit will use the nominal visit label. This will allow for correct classification of Visit 6 (pre-vaccination antibody measure), Visit 7 (EOT), and Visit 8 (End of Study) at different time points for different participants due to influenza vaccination delay should it occur, as described in section [3.3.1](#).

Participants who discontinue study intervention early should attend all further study visits as defined in the CSP, hence any collected data will be used as planned.

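### The tezepelumab trough summary has no limit on time since the last dose, so samples taken 8 weeks or more after dosing stopped can enter the Week 12 and Week 16 figures as troughs

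*SAP*

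**What the plan says.** Protocol Table 3 makes the serum trough a secondary endpoint, and Protocol 2.1 lists "serum trough tezepelumab concentrations" among the things to be investigated. SAP 4.2.2.2 adds that "the PK assessment will be based on the observed serum trough concentrations". Neither document defines a trough by time since dose.

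SAP 4.2.2.4.1 summarises concentrations at each visit under two conditions:

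- "Only samples collected prior to the first study intervention dose for baseline samples"
- "Only samples collected prior to influenza vaccination administration for pre-vaccination samples"

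The second condition does keep the Visit 6 sample ahead of that day's dose, because the Schedule of Activities states: "Influenza vaccine is to be administered after scheduled blood samples are taken and prior to study intervention administration". Visits 7 and 8 have no condition.

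On visit assignment, SAP 3.3.2 states: "All summaries and analyses which are presented by visit will use the nominal visit label". On participants who stop early, it says they "should attend all further study visits as defined in the CSP, hence any collected data will be used as planned". Protocol 7.1 likewise encourages them to keep attending, and the Schedule of Activities has PK samples at Visits 6, 7 and 8 and at the discontinuation (IPD) visit.

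One filter could act on this. The PK analysis set (SAP Table 1) is limited to data assumed to be free of the influence of factors such as protocol deviations, and SAP 3.3.5 lets deviations exclude from that set. Which deviations count is left to a separate specification.

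**The concern.** A trough under 4-weekly dosing is the level about 4 weeks after a dose. Without a rule on time since dose, the nominal visit label decides what counts. A participant who received the Week 8 dose but not the Week 12 dose and attends Visit 7 gives an 8-week sample that is summarised with the Week 16 troughs. Stopping study intervention is allowed by the protocol and is not in itself a deviation, so the PK-set filter does not clearly remove that sample.

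Vaccination is placed at Week 12 because steady state is expected by then (Protocol 4.1). The Visit 6 and Visit 7 concentrations are the direct evidence that the tezepelumab arm had the intended exposure when it was vaccinated and when the response was measured. Off-dose samples pull the geometric mean down and push the geometric coefficient of variation (GCV) up. A reader comparing these figures with troughs from other tezepelumab studies would not be comparing like with like.

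**Working it through.** The plan states no PK figure to reproduce, so the check is a size estimate.

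**Inputs**

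- Half-life: Protocol 5.3 equates 16 weeks with 5 half-lives, so 16/5 = 3.2 weeks.
- Doses at Weeks 0, 4, 8 and 12; samples at Week 12 (before that day's dose) and Week 16.
- About 100 randomized 1:1, so 50 per arm.
- Model (assumption): equal doses, first-order decay, superposition, absorption ignored.

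**Fraction left after 4 weeks:** r = 2^(−4/3.2) = 0.420.

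**Full-dosing trough, in units of one dose**

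- Week 12: r + r² + r³ = 0.420 + 0.177 + 0.074 = 0.672
- Week 16: r + r² + r³ + r⁴ = 0.672 + 0.031 = 0.703

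Consistency check: the Week 12 trough is 1 − r³ = 0.926 of steady state, which fits the protocol's statement that steady state is reached by Week 12.

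**Level relative to full dosing after stopping**

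| Last dose | Visit 6: weeks since dose | Visit 6: ratio | Visit 7: weeks since dose | Visit 7: ratio |
|---|---|---|---|---|
| Week 8 | 4 | 1.000 | 8 | (r²+r³+r⁴)/0.703 = 0.402 |
| Week 4 | 8 | (r²+r³)/0.672 = 0.374 | 12 | (r³+r⁴)/0.703 = 0.150 |
| Week 0 | 12 | r³/0.672 = 0.111 | 16 | r⁴/0.703 = 0.044 |

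Varying the half-life from 2.8 to 3.7 weeks (assumption), the Visit 6 ratios run 0.338 to 0.410 and 0.091 to 0.132. The Visit 7 ratios run 0.359 to 0.445, 0.121 to 0.183 and 0.033 to 0.059.

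**Effect of one such participant in 50 on the geometric mean:** factor = ratio^(1/50).

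- Visit 6: 0.374^0.02 = 0.981 and 0.111^0.02 = 0.957, a fall of about 2% or 4%.
- Visit 7: 0.402^0.02 = 0.982, 0.150^0.02 = 0.963 and 0.044^0.02 = 0.940, a fall of about 2%, 4% or 6%.

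**Scenario with a rate from the documents.** Protocol 2.2 reports that 6.8% discontinued tezepelumab in a 52-week Phase 3 study. If 6.8% of this arm had stopped and still attended Visit 7, the geometric mean factor would be 0.940, 0.879 or 0.809 (last dose Week 8, 4 or 0), a fall of about 6% to 19%. The arithmetic mean would fall by about 4% to 7%. The treatment period here is far shorter, so this is a generous rate.

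**Effect on the GCV.** Assume an on-treatment GCV of 40%, so the log variance is ln(1.16) = 0.148. With 3 of 50 off-dose samples, add 0.06 × 0.94 × (ln ratio)².

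- Last dose Week 8: 0.148 + 0.0564 × 0.83 = 0.195, so GCV = √(e^0.195 − 1), about 46%.
- Last dose Week 0: 0.148 + 0.0564 × 9.7 = 0.695, so GCV is about 100%.

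**Skipped doses.** A participant who misses only Week 8 is at 0.374 at Visit 6 and (r + r³ + r⁴)/0.703 = 0.748 at Visit 7.

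**The case against.** The strongest reply has five parts.

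1. The PK-set filter may already remove some of these samples. This stands for skipped doses. A reader might infer that they are certain to be averaged in, but the documents do not say whether a skipped dose excludes a sample. It does not stand for permitted discontinuation, which is not in itself a deviation, although the filter's open wording leaves some room.

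2. The most extreme Visit 7 case is uncertain. After a last dose at Week 0, the 16-week follow-up visit falls on the Visit 7 date, and Protocol 7.1 then calls for the follow-up assessments plus the influenza antibodies. The PK sample may be labelled as follow-up, so a reader should not take it as settled that the 0.04 value is summarised under Week 16. The Week 4 and Week 8 cases do not have this overlap.

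3. A sample is not washout merely because dosing has stopped. The IPD sample, and the Visit 6 sample after a last dose at Week 8, are true 4-week troughs. This stands, and any rule must keep them.

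4. The SAP table does not call the Visit 8 value a trough. This also stands; for Visit 8 the point is only one of labelling.

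5. The primary estimand retains participants who discontinue, so an all-sample summary describes the exposure of the population whose vaccine response is estimated. This is a good reason to keep that table. It is not a reason to present it as the trough endpoint.

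The endpoint is also secondary and descriptive, and the median, minimum and maximum are reported too.

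**Conclusion.** The gap is real: the endpoint is a trough, yet nothing in the summary rules ties a sample to the time since the last dose, and data after discontinuation are kept under the nominal label. Followed as written, the rules bias the trough mean downwards and the GCV upwards whenever participants stop and keep attending. The size is modest per participant and grows with the number who stop and how early they do so. It rests on a simple decay model, on the half-life implied by the protocol, and on an assumed number and timing of discontinuations. The top of the Visit 7 range also requires the Week-0-only sample to be labelled Visit 7. The documents do not support saying that every sample after stopping is washout. No primary result depends on this summary, but the change is worth making before the table is produced.

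**What to change.** Add a third condition to SAP 4.2.2.4.1: Visit 6 and Visit 7 concentrations enter the trough summary only if taken about 4 weeks after the last dose, within the protocol's visit windows. With ±3 days at both the dosing visit and the sampling visit, that is 28 ± 6, or 22 to 34 days. Because the rule is worded by time since the last dose, it keeps a Visit 6 sample after a Week 8 last dose and works unchanged if vaccination is delayed.

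Alongside it:

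- keep the all-sample by-visit summary as a supporting table;
- list off-window samples with actual time since last dose, and flag in-window samples that follow an earlier skipped dose;
- label Visit 8 as follow-up concentration;
- state which deviations exclude a participant or sample from the PK analysis set.

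The cost is a few sentences in the SAP and one variable derived from dosing and sampling dates. The downside is slightly fewer samples in the trough table. Nothing is lost from reporting, and no trial procedure changes.

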4.2.2.4.2 Analysis of immunogenicity

ADA to tezepelumab will be summarized using descriptive statistics at each visit by treatment group.

The ADA status across the study for each subject will also be classified and summarized by treatment group. Specifically, the following ADA results will be evaluated as number and proportion of subjects in cohorts together with corresponding titre summaries. However, if the number of ADA positive subjects in the safety analysis set is small then the ADA variables may be listed only in the CSR:

- Subjects who are ADA positive at any time including baseline (ADA prevalence).
- Subjects who are ADA positive at baseline only.
- Subjects who are ADA positive at baseline and positive in at least one post baseline measurement.
- Subjects who are ADA positive at baseline regardless of post-baseline result.
- Subjects who are ADA positive post-baseline.
- Subjects who are ADA positive post-baseline and ADA negative at baseline (treatment induced ADA)
- Subjects who are persistently positive; persistently positive is defined as having at least two post-baseline ADA positive measurements (with ≥ 16 weeks between first and last positive) or an ADA positive result at the last available post-baseline assessment.
- Subjects who are transiently positive; transiently positive is defined as having at least one post-baseline ADA positive measurement and not fulfilling the conditions for persistently positive.
- Subjects with treatment boosted ADA, defined as baseline positive ADA titre that was boosted to a 4-fold or higher level following study intervention administration
- Subjects with treatment emergent ADA (ADA incidence): defined as the sum of treatment induced ADA and treatment boosted ADA.

For ADA summaries at a single time point (e.g. baseline ADA or by visit) the corresponding titre summary will be based on the titre of the positive sample for that particular visit.

For summaries across visits (e.g. ADA positive at any visit) the corresponding titre summaries will be based on the maximum titre of all positive samples for each subject.

[figure not shown]
Neutralizing ADA evaluations will be conducted on confirmed ADA positive samples. The test sample is deemed positive or negative for the presence of neutralizing antibodies (nAb) to tezepelumab relative to a pre-determined (in assay validation) statistically derived cut point. The number and proportion of subjects who are nAb positive at any time will be evaluated.

If appropriate, the association of ADA status across the study with primary and key secondary efficacy, biomarkers and AEs/serious AEs (SAEs) may be evaluated.

[figure not shown]
CCI

CCI

CCI

CCI

4.3 Pharmacodynamic Endpoint(s)

Refer to section [4.6.34.2.2](#) for details.

4.4 Pharmacokinetics

Refer to section [4.2.2](#) for details.

4.5 Immunogenicity

Refer to section [4.2.2](#) for details.

4.6 Safety Analyses

The domain safety covers exposure, adverse events, clinical laboratory, and vital signs.

Tables are provided for the safety analysis set; listings are provided for all participants or the safety analysis set depending on the availability of data.

4.6.1 **Exposure**

4.6.1.1 **Definitions and Derivations**

Duration of exposure to study intervention is defined as the number of days between the date of first dose and the date of last dose of study intervention inclusive, calculated as follows:

Duration of exposure (days)

$$\begin{aligned} &= \text{minimum}(\text{date of last dose of study intervention} \\ &\quad + 33 \text{ days; date of death; date of study withdrawal}) \\ &\quad - \text{date of first dose of study intervention} + 1 \end{aligned}$$

This calculation does not consider any gaps in exposure caused by the participant missing one or more intermediate scheduled weekly doses. Such cases will be identified in the CSR if they occur but will not explicitly be accounted for in any analysis. Date of last dose will include the unscheduled visits due to delayed flu vaccine administration, if applicable.

4.6.1.2 **Presentation**

Duration of exposure (days) will be summarized by treatment group and presented for the safety analysis set.

4.6.2 **Adverse Events**

4.6.2.1 **Definitions and Derivations**

Adverse Events (AEs) will be summarized for analysis according to their onset date into the following study periods:

- AEs occurring during screening: date of Visit 1 \leq AE onset date $<$ date of first dose of study intervention
- AEs occurring during on-treatment period: date of first dose of study intervention \leq AE onset date \leq minimum (date of last dose of study intervention +33 days, date of death, or date of study withdrawal)
- AEs occurring during on-study period: date of first dose of study intervention \leq AE onset date \leq study completion or date of study withdrawal.

Rules for imputing AE start/stop dates which are partially missing can be found in [Appendix A: Partial Date Conventions for Adverse Events](#). Partially missing start/stop dates will appear as such in the participant data listings but will be imputed to permit proper tabulation of AE data.

AEs of special interest (AESIs) are an event of scientific and medical interest towards improving the understanding of the study intervention. An AESI may be serious or non-serious. Similar considerations apply to any additional supporting analysis of AESIs, in which MedDRA dictionary-based definitions are used. Derivation details (for those derived from the eCRF), or a statement when the derivation needs to be referenced externally to the SAP (for those derived from MedDRA dictionary terms), are given in Appendix [7.3](#).

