3 DATA ANALYSIS CONSIDERATIONS

3.1 Timing of Analyses

There is neither an unblinded data review nor interim analysis planned for this study prior to primary database lock. There will be two database locks in this study. The primary database lock and analysis will be conducted after the last participant (enrolled in the 2021/2022 flu season) completes Visit 7 (Week 16), and the final database lock and analysis will be conducted once all participants have completed the follow-up period, Visit 8 (Week 28). All analyses of the primary objectives and selected safety objectives will be performed based on the primary database lock data.

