3.3.1 General Study Level Definitions

Unless stated otherwise, continuous variables will be summarized by descriptive statistics (number of participants [n], arithmetic mean, standard deviation (SD), minimum, median and maximum). Categorical variables will be summarized in frequency tables (frequencies and percentages).

Mean(s), median(s), SD(s) and quartiles (where applicable) will be displayed with one more decimal place than the collected data. Minimum(s) and maximum(s) will be displayed with the same number of decimal places as the collected data. For discrete variables, population size (N for analysis set size and n for available data) and percentage will be presented. Percentages will be displayed with one decimal place.

As no statistical testing is planned, no p-values will be presented.

If influenza vaccine administration is delayed, an additional one to two study intervention doses may be administered to participants during unscheduled visits prior to visit 6 (as needed) until the influenza vaccine is available at study sites. Throughout this document End of Treatment (EOT) refers to the end of treatment visit, which is four weeks after the last dose of study intervention and could be either week 16, 20 or 24 for each participant. The end of study visit is 16 weeks after last dose of study intervention.

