4.1.8 Prior and Concomitant Medications

4.1.8.1 Definitions and Derivations

A list of permitted, restricted and prohibited medications can be found in section 6.5 of the CSP. Please refer to [Appendix B: Imputation Rules for Missing/Partially Missing Prior/Concomitant Medication](#) for the method of imputation of missing concomitant medication onset/start and end/stop dates.

Medications will be categorized for analysis according to their onset and end dates as follows:

- Prior medications:
 - end date \leq date of first dose of study intervention
- Concomitant medications during on-treatment period:
 - end date $>$ date of first dose of study intervention and start date \leq minimum (date of last dose of study intervention + 33 days, date of death, date of study withdrawal), or
 - end date ongoing and start date \leq minimum (date of last dose of study intervention + 33 days, date of death, date of study withdrawal)
- Concomitant medications during post-treatment period (for subjects still being followed up then):

- start date > date of last dose of study intervention + 33 days.

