4.1.9.2 Presentation

Treatment compliance will be summarized by treatment group and presented for the full analysis set. The date and time of study intervention administrations, and all missed doses will be listed.

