4.6.2.2 Presentation

All AE summaries will be presented by actual treatment group for the safety analysis set. A by- participant listing of all AEs will be provided; AEs occurring during screening will be included in the listing, but not summarized separately. The number and percentage of participants with on-treatment and on-study AEs will be tabulated separately by system organ class and preferred term. An event that occurred one or more times during a period will contribute one observation to the numerator of the proportion. The denominator of the proportion will comprise all participants in the safety population. On-treatment AEs will also be summarized by intensity/severity and separately, by causality/relatedness (as determined by the investigator). Should a participant report the same preferred term/system organ class within multiple intensity/severity or causality/relatedness categories, the participant's worst occurrence (most severe/most related) will be tabulated. Serious AEs, AEs leading to death, AEs leading to discontinuation from study intervention, and commonly occurring AEs (defined as those occurring in >5% of subjects in either treatment group) will be summarized by treatment group. AESIs will also be summarized descriptively by treatment group; serious infections will be summarized as part of the SAE by SOC and PT table in the SOC of infections and infestations and not in a separate table.

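### Does the SAP leave duration of exposure undefined because its sentence stops at the last dose while its formula adds up to 33 days?

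*SAP*

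**What the plan says.** SAP section 4.6.1.1 opens with a verbal definition of exposure: "the number of days between the date of first dose and the date of last dose of study intervention inclusive". It then introduces a formula as the way to calculate that quantity. The formula takes the minimum of three dates (last dose plus 33 "days; date of death; date of study withdrawal"), subtracts the date of first dose and adds one. The text after the formula says that gaps from missed doses are ignored and that unscheduled doses given because of vaccine delay count towards the last dose. It does not comment on the 33 days. It also calls the scheduled doses weekly, although dosing is every 4 weeks in Protocol section 4.1.

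The same end point appears twice more. The on-treatment period for adverse events (SAP 4.6.2.1) closes at "minimum (date of last dose of study intervention +33 days, date of death, or date of study withdrawal"). The on-treatment period for concomitant medications (SAP 4.1.8.1) closes at "minimum (date of last dose of study intervention + 33 days, date of death, date of study withdrawal").

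The result is summarized by treatment group in the safety analysis set (SAP 4.6.1.2). The documents give no numerical exposure duration.

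**The concern.** A definition and its formula should describe the same quantity, and here they do not. Someone reading the table with only the verbal definition would take the figure as the span from first to last injection and would overstate that span by up to 33 days. A single-dose participant would appear to have 34 days of exposure, not 1.

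The number of doses can also vary. If the vaccine is delayed, one or two extra doses may be given, so end of treatment "could be either week 16, 20 or 24 for each participant". A misread duration could then blur planned and extended treatment. The reference to weekly doses in the same paragraph adds to the impression that the text was not checked against this trial's schedule.

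At stake would be the interpretation of a safety exposure table and, if exposure served as a denominator, the adverse event rates as well.

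**Working it through.** **Inputs.** Doses at Weeks 0, 4, 8 and 12 (Protocol 4.1), so the last planned dose falls 84 days after the first. One or two extra doses at 4-week intervals if the vaccine is delayed (Protocol 4.1, SAP 3.3.1), so the last dose falls at day 112 or 140. The tail is 33 days (SAP 4.6.1.1). There is no stated exposure figure to reproduce.

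**Rules.** Sentence: last dose − first dose + 1. Formula: min(last dose + 33, death, withdrawal) − first dose + 1.

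**Results, with no death or withdrawal within 33 days of the last dose:**

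| Doses | Sentence | Formula | Gap |
|---|---|---|---|
| 1 | 0 + 1 = 1 | 0 + 33 + 1 = 34 | 33 |
| 4 (planned) | 84 + 1 = 85 | 84 + 33 + 1 = 118 | 33 (33/85 = 38.8%) |
| 5 | 112 + 1 = 113 | 112 + 33 + 1 = 146 | 33 (33/113 = 29.2%) |
| 6 | 140 + 1 = 141 | 140 + 33 + 1 = 174 | 33 (33/141 = 23.4%) |

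**With an early end.** Withdrawal 10 days after the Week 12 dose gives 85 by the sentence and 84 + 10 + 1 = 95 by the formula. Withdrawal on the day of that dose gives 85 by both.

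**Which rule operates.** The sentence hands over to the formula, and the text after it goes on to discuss that calculation. The formula is explicit and can be programmed as it stands. Its end point is the one in SAP 4.6.2.1 and 4.1.8.1, so exposure time by the formula covers the same days as the adverse event on-treatment window. The sentence alone would credit a single-dose participant with one day on a 4-weekly regimen, while the SAP counts that participant's adverse events as on-treatment for up to 33 days after the dose. The formula is the consistent reading.

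**Does the choice alter comparisons?** Within either rule, participants with four, five and six doses stay in order and 28 days apart: 85, 113, 141 or 118, 146, 174. One table uses one rule, so it would never set a four-dose formula value (118) beside a five-dose sentence value (113). For anyone not cut short by death or withdrawal, the two rules differ by a constant 33 days, so the dosing span is recovered by subtraction. Between arms, the difference in means can move only through participants who die or withdraw within 33 days of their last dose. As an illustration, with 50 participants per arm (Protocol 9.2), one such withdrawal on the last-dose date shifts that arm's mean tail by 33/50 = 0.66 days.

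**Does anything else use it?** For adverse events, "The denominator of the proportion will comprise all participants in the safety population". The SAP describes no rate per unit of exposure, and the primary endpoints are titers, fold rises and responder proportions.

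**The case for a change.** The strongest reply is that the SAP presents sentence and formula as one quantity and never says which governs, so preferring the formula is an inference. It can be added that this table is the only summary of how long participants were treated. The compliance measure in SAP 4.1.9.1 cannot show it, because expected doses are counted only up to each participant's own last dosing visit. A one-dose and a six-dose participant with no missed visits both score 100%.

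Both observations are correct. The inference is a strong one, though: only the formula is specific enough to program, and two other sections share its end point. The compliance measure is indeed silent on duration, but dosing spans are not lost: "The date and time of study intervention administrations, and all missed doses will be listed". A second exposure variable measuring the dosing span would be a presentational preference.

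A related worry is the primary lock, since "All analyses of the primary objectives and selected safety objectives will be performed based on the primary database lock data". Visit 7 is nominally 28 days after the last dose, so for the last participant the formula could run 33 − 28 = 5 days past that visit, or 11 if the ±3-day windows at Visits 6 and 7 bring the two visits as close as 22 days. This is a separate matter from the wording. The SAP neither places exposure among the selected outputs nor defines a data cut-off date, and the effect would be a few days in a descriptive summary.

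The word weekly does conflict with the 4-weekly schedule, and the passages should be reconciled whenever the SAP is next opened. The formula contains no dosing interval, so no figure depends on it.

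**Conclusion.** The lead-in sentence does not describe its own formula, and the gap is 33 days for any participant who neither dies nor withdraws within 33 days of the last dose: 85 against 118 days for a planned completer. This is a clerical slip with no statistical consequence. A programmer has one explicit formula, consistent with the on-treatment windows elsewhere in the SAP. Correcting the sentence would leave every computed value as it is.

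The conclusion assumes that the formula is implemented as written and that exposure remains a descriptive summary with the same rule in both arms, as the documents show. If exposure time were later used as a denominator for event rates, the choice of end date would matter and should be stated. Nothing in the plan calls for that, so no change follows.
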